#### **4.4.2.3 Improvement in Endoscopic Appearance of the Mucosa**

The proportion of patients with improvement in endoscopic appearance of the mucosa at Week 62 will be analyzed using the same methods as the primary endpoint. Definition of improvement in the appearance of the endoscopic mucosa is provided in the project SAP, Section 4.4.2.

#### **4.4.2.4 Remission at Week 62 (Among Patients in Remission at Week 10)**

The proportions of patients who achieved remission at Week 62 given they achieved remission at Week 10 will be analyzed using the same methods as the primary endpoint, and include patients randomized into the maintenance mITT population. Due to low number of patients in this analysis the stratification factor IS use after Week 10 will not be included in the model, to prevent any strata with no values impacting the analysis. The definition of remission is the same at each time point and is described in project SAP, Section 4.4.2.1.4.

**Proportion of patients in remission at Week 62 among patients in remission at Week 10**

$$= \frac{\text{\# of patients in remission at Week 10 and Week 62}}{\text{\# of patients in remission at Week 10}}$$

#### **4.4.2.5 Endoscopic Remission**

The proportion of patients with endoscopic remission at Week 62 will be analyzed using the same methods as the primary endpoint. Definition of endoscopic remission is provided in the project SAP, Section 4.4.2.1.4.

#### **4.4.2.6 Histologic Remission**

The proportion of patients with histologic remission at Week 62 will be analyzed using the same methods as the primary endpoint using the histology evaluable population.

Definition of histologic remission is described in the project SAP, Section 4.4.2.2. Further details of additional analysis to support this endpoint using different scoring systems are detailed in the project SAP, Section 4.4.2.2.

#### **4.4.2.7 UC-PRO/SS**

Details of UC-PRO/SS endpoints and the analyses are provided in the project SAP, Section 4.4.2.3. The change from baseline at Week 62 in both the functional and bowel domains will be analyzed separately.

#### **4.4.2.8 Corticosteroid-Free Clinical Remission at Week 62 (Off Corticosteroid for At Least 24 Weeks Prior to Week 62) in Patients Who Were Receiving Corticosteroids at Baseline**

This endpoint will be analyzed using the same methods as Section 4.4.2.2. Remission will be substituted with Clinical Remission. Clinical Remission is determined by the MCS and described in the project SAP, Section 4.4.2.1.4. As detailed in [Figure 2](#) (Section 4.4.2.1), this endpoint is not included in the multiple testing procedure for endpoints.

#### **4.4.2.9 Clinical Remission at Week 62 (Among Patients in Clinical Remission at Week 10)**

The endpoint will be analyzed using the same methods as Section 4.4.2.4. Remission will be substituted with clinical remission. Clinical Remission is determined by the MCS and described in the project SAP, Section 4.4.2.1.4. As detailed in [Figure 2](#) (Section 4.4.2.1), this endpoint is not included in the multiple testing procedure for endpoints.

#### **4.4.2.10 Clinical Remission**

Definition of clinical remission is provided in the project SAP, Section 4.4.2.1.4. The proportion of patients in clinical remission at Week 62 will be analyzed using the same methods as the primary endpoint. As detailed in [Figure 2](#) (Section 4.4.2.1), this endpoint is not included in the multiple testing procedure for endpoints.

#### **4.4.2.11 Clinical Response**

Definition of clinical response is provided in the project SAP, Section 4.4.2.1.4. The proportion of patients in clinical response at Week 62 will be analyzed using the same methods as the primary endpoint. As detailed in [Figure 2](#) (Section 4.4.2.1), this endpoint is not included in the multiple testing procedure for endpoints.

#### **4.4.2.12 Inflammatory Bowel Disease Questionnaire (IBDQ)**

Details of the IBDQ endpoint and the analyses are provided in the project SAP, Section 4.4.2.4. The change from baseline at Week 62 in IBDQ will be analyzed. As detailed in [Figure 2](#) (Section 4.4.2.1), this endpoint is not included in the multiple testing procedure for endpoints.

#### **4.4.3 Exploratory Efficacy Endpoints**

Exploratory endpoints detailed in the protocol will also be analyzed. Binary endpoints will use the same statistical methods used for the primary endpoint. Continuous endpoints will use the same statistical methods used for the change from baseline key secondary endpoints.

#### **4.4.4 Sensitivity Analyses**

To support the primary analyses the following sensitivity analyses will be conducted: definitions of partial Mayo Clinic Score (pMCS) and mMCS are included in the project SAP, Section 4.4.2.1.4.

- Proportion of patients in remission at Week 62 among clinical responders at Week 10 (remission derived using mMCS including mild friability in Mayo ES = 1)
- Proportion of patients in remission at Week 62 among clinical responders at Week 10 (remission derived using pMCS)
- Proportion of patients in remission at Week 62 among clinical responders at Week 10 (difference in proportions calculated using Fisher's exact test)
- Proportion of patients in remission (mMCS) at Week 62 among clinical responders (mMCS) at Week 10 (excluding friability from Mayo ES = 1)
- Proportion of patients in remission at Week 62 among clinical responders at Week 10 (Tipping Point Analysis)

All key secondary endpoints included in [Figure 2](#) which are calculated using MCS or the endoscopic subscore will be re analyzed as a sensitivity analyses using the modified Mayo Clinic Score (mMCS) excluding friability from ES = 1 or the endoscopic subscore excluding friability from ES = 1 if applicable. This analysis will be conducted on the mITT population and are listed below.

- Proportion of patients corticosteroid free remission at Week 62 (Off corticosteroid for at least 24 weeks prior to Week 62) in patients who were receiving corticosteroids at baseline (remission derived using the mMCS excluding mild friability in Mayo ES = 1)
- Proportion of patients with improvement of endoscopic appearance of the mucosa at Week 62 (endoscopic score excluding mild friability in Mayo ES = 1)
- Proportion of patients remission at Week 62 among patients in remission at Week 10 (remission at Week 10 and Week 62 derived using the mMCS excluding mild friability in Mayo ES = 1)

#### **4.4.5 Supplementary Analyses**

To support the primary analyses the following supplementary analyses will be conducted;

- Proportion of patients in remission at Week 62 among clinical responders at Week 10 (including data collected whilst patients received rescue therapy)

- Proportion of patients in remission at Week 62 among clinical responders at Week 10 (using logistic regression model)
- Proportion of patients in remission at Week 62 among clinical responders at Week 10 (using clinical database derivation of clinical response at Week 10, if appropriate)

Definitions of clinical response are included in the project SAP, Section 4.4.2.1.4.

#### **4.4.6            Subgroup Analyses**

Subgroup analyses are detailed in the project SAP, Section 4.4.3.

### **4.5                PHARMACOKINETIC AND PHARMACODYNAMIC ANALYSES**

Details are included in the project SAP, Section 4.5.

### **4.6                SAFETY ANALYSES**

Data reported during the Induction Phase using the induction safety population will include data for all patients enrolled into the Induction Phase, up until they are randomized into the Maintenance Phase. For patients who are not randomized into the Maintenance Phase, data will be reported up until the patient completes/withdraws from the study. If a patient is ongoing in the Induction Phase due to being in safety follow-up at the time of the primary data analyses, all available data at time of the primary analyses CCOD will be reported.

Data reported during the Maintenance Phase will include data for all patients in the maintenance safety population up until the patient complete/withdraws from the study. All safety analyses using the maintenance safety population data will be reported from baseline. Baseline is defined as the last available assessment prior to first receipt of study drug at the beginning of the Induction Phase. If a patient is ongoing in the Maintenance Phase due to being in safety follow-up at the time of the primary data analyses, all available data at time of the primary analyses CCOD will be reported.

Further details of the safety analyses are included in the project SAP, Section 4.7.

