Appendix 1 Schedule of Activities (cont.)

- cc Paxgene blood RNA samples must be collected after all other blood and serum samples.
- dd With the exception of Week 0, the IBDQ and the EQ-5D will be completed in-clinic by the patient after the PML neurological examination but before any other non-PRO assessments and before the patient receives any disease status information or study drug during that visit.
- ee Randomization to occur within 2 weeks starting from Week 10 timepoint.
- ff Where indicated, patients must be instructed to administer study drug at home within 3 days (maximum) after clinic visit.

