##### **4.1.1.3 Safety Population**

The safety analysis population for the Induction Phase will include all patients who received at least one dose of etrolizumab during the Induction Phase.

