#### **4.1.2.4 Safety Population**

The safety analysis population for the Maintenance Phase will include all patients who receive study drug in the Maintenance Phase. Patients will be included in the treatment arm for the treatment most frequently received during the Maintenance Phase.

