- Injection site reactions – Events identified using the eCRF tick box indicating an Injection site reaction AND/OR events occurred in the MedDRA Injection Site Reaction High Level Term (HLT) using both primary and secondary coding.

Outputs will be summarized using the safety population split by treatment arm and cohort as appropriate.

Summaries of AEs will be generated to summarize the incidence of treatment-emergent AEs only. Treatment-emergent events are defined as any new AE reported or any worsening of an existing condition on or after the first dose of study drug. If the onset date of the AE is prior to the day of first dose, the AE will be considered treatment-emergent only if the most extreme intensity is greater than the initial intensity (i.e., the intensity for a given AE increases and its end date is on or after the date of the first dose). Non-treatment emergent AE's collected in the database will also be reported separately, for each individual CSRs.

For each treatment group, the incidence count for each AE preferred term will be defined as the number of patients reporting at least one treatment-emergent occurrence of the

event (multiple occurrences of the same AE in one patient will be counted only once). The proportion of patients with an AE will be calculated as the incidence count divided by the total number of patients in the population. Each table will also present the total number of AEs reported where multiple occurrences of the same AE in an individual are counted separately.

The rate per 100 patient years and 95% CIs will be summarized by treatment group for studies (GA28950, GA29102, GA29103, GA28948, and GA28949). Rates will be calculated for AEs, SAEs, and other AE grouping as appropriate. The rate of AEs per 100 patient years is calculated as:

$$= \frac{\text{Total Number of AEs}}{\text{Total Number of Patient Years at Risk}} \times 100$$

All summaries and listings of AEs will be based on the induction safety population or the maintenance safety population and listed in the List of Planned Outputs (LoPO).

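### Study SAP 4.6 leaves adverse events after randomisation outside both phase summaries for a patient who is randomised but never dosed in maintenance

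*SAP*

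**What the plan says.** Study SAP 4.1.1.3 puts every patient who "received at least one dose of etrolizumab during the Induction Phase" into the induction safety population. Study SAP 4.6 then sets the time window. Data in that population are reported "up until they are randomized into the Maintenance Phase". One group is exempt from the cut: "For patients who are not randomized into the Maintenance Phase, data will be reported up until the patient completes/withdraws from the study".

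For the second phase, Study SAP 4.6 says: "Data reported during the Maintenance Phase will include data for all patients in the maintenance safety population". Study SAP 4.1.2.4 defines that population; it "will include all patients who receive study drug in the Maintenance Phase". The start of the maintenance window is also fixed: "All safety analyses using the maintenance safety population data will be reported from baseline", and baseline means before the first induction dose.

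Project SAP 4.7.1 provides no third set: "All summaries and listings of AEs will be based on the induction safety population or the maintenance safety population".

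Protocol Appendix 1, footnote ee, gives the timing: "Randomization to occur within 2 weeks starting from Week 10 timepoint". Protocol 4.3.2.1 places the third dose at Week 8 and the fourth at Week 12. Protocol 6.5 defines the safety set as everyone dosed at least once in induction, calls for separate AE summaries by phase, and states no cut at randomisation.

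**The concern.** The induction window closes at one event (randomisation), while entry to the maintenance set depends on a later one (a maintenance dose). A patient who passes the first and never reaches the second is cut from one summary without entering the other. The SAP foresees such patients: its mITT definition (Study SAP 4.1.2.1) requires a maintenance dose in addition to randomisation.

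These patients were exposed to open-label etrolizumab, and under Protocol 5.3.1 their AEs are collected until the last study visit. At stake is whether the AE tables for an etrolizumab-exposed group are complete, as Protocol 6.5 would lead a reader to expect.

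**Working it through.** The plan states no figure on this point, so there is none to reproduce. The check applies the rules to each type of patient and then works out the length of the uncovered period from the visit schedule.

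**Rules by patient type**

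| Patient | Induction summary | Maintenance summary | AEs after Week 10 |
|---|---|---|---|
| (a) Not randomised | To completion or withdrawal | Not a member | Covered |
| (b) Randomised and dosed in maintenance | To randomisation | Member, reported from study baseline | Covered, including the days between randomisation and first maintenance dose |
| (c) Randomised, never dosed in maintenance | To randomisation | Not a member | In neither summary after randomisation |

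A type (c) patient remains a member of the induction safety population. It is the date window, not membership, that removes the later events.

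**Length of the uncovered period for type (c)**

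Inputs:
- Last induction dose: Week 8 (Protocol 4.3.2.1).
- Randomisation: Weeks 10 to 12 (Protocol 3.1.1 and Appendix 1, footnote ee).
- Safety follow-up: 12 weeks, with visits timed from the last dose (Protocol 4.5.2.4).

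Steps:
- End of follow-up = 8 + 12 = Week 20.
- Uncovered if randomised at Week 10: 20 − 10 = 10 weeks.
- Uncovered if randomised at Week 12: 20 − 12 = 8 weeks.
- Time since last dose: from 10 − 8 = 2 weeks at the earliest to 20 − 8 = 12 weeks at the latest.

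This takes visits on their nominal weeks and assumes follow-up is completed. A patient who leaves sooner has a shorter gap.

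**Number of patients**

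Neither document gives one. Purely for scale, an assumed 0 to 3% of the planned 210 randomised patients would be 0 to about 6 (0.03 × 210 = 6.3).

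**Whether another rule closes the gap**

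- Project SAP 4.7 adds patients who were dosed without being randomised, which is the reverse case.
- Study SAP 4.6 reports all available data for patients still in safety follow-up at the clinical cutoff. That reaches only those still in follow-up then; a follow-up ending at Week 20 will normally be over long before the last patient reaches Week 62.
- Study SAP 2.4 promises later analyses of all AEs, including those from the 12-week follow-up, but names no population or window that overrides Study SAP 4.6 and Project SAP 4.7.1.

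**The case against.** The best defence is that this is a narrow matter of definition with strong backstops, and most of that stands. Project SAP 4.8 reports all deaths. Project SAP 4.7.1 requires narratives for deaths, serious AEs, AEs leading to treatment discontinuation, pregnancies, serious and opportunistic infections, and malignancies. Study SAP 2.4 and Project SAP 4.7 both speak of using all AE or safety data, and the list of planned outputs, which is not among these documents, may be more complete than the text. Protocol 6.5 itself asks for summaries by phase and leaves detail to the SAP, so the departure from it concerns a window boundary and not who belongs to the safety set.

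A reader might infer three stronger things that the documents do not support.

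- *That these events vanish from all reporting.* The deaths rule and the narratives rule this out for the most important cases.
- *That the lost events are selected for being safety events, because those are what would stop the Week 12 dose.* Protocol Table 5 lets study drug restart after a serious infection resolves, Protocol 5.1.2.2 lets dosing resume once PML is ruled out, and Protocol 4.3.2.1 allows a short delay for minor illness. A patient dosed late becomes type (b) and loses nothing. A patient may also go undosed for an unrelated reason such as withdrawal of consent (Protocol 4.6.1). Informative loss is possible but not shown.
- *That every randomised patient has a hole between randomisation and Week 12.* Reporting maintenance safety from baseline prevents this.

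What survives is that narratives and the deaths rule do not put events into incidence tables or rates per 100 patient-years, and they do not reach non-serious AEs that led to no discontinuation.

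**Conclusion.** The gap is real and confined to patients who are randomised but receive no maintenance dose. Applied as written, the rules leave their AEs after randomisation out of both phase summaries, for up to about 8 to 10 weeks per patient. That range rests on a Week 8 last dose, randomisation at Weeks 10 to 12, and completed follow-up counted from the last dose. The loss falls mainly on incidence counts, rates per 100 patient-years and non-serious AEs. The number affected is undocumented, probably small and possibly zero. No efficacy result depends on it, and nothing in the documents shows that a safety conclusion would change. It still merits correction: the SAP anticipates this type of patient, Protocol 6.5 includes them, and their data are already collected.

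**What to change.** In Study SAP 4.6, change the condition that opens the sentence "For patients who are not randomized into the Maintenance Phase, data will be reported up until the patient completes/withdraws from the study" so that it turns on dosing and not on randomisation. For example: *For patients who do not receive study drug in the Maintenance Phase, whether or not randomised, data are reported in the induction summary until study completion or withdrawal.* The preceding sentence, which cuts at randomisation, should then be limited to patients who go on to a maintenance dose.

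The induction cut-off for dosed patients need not move, since their events are already in the maintenance summary.

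The cost is one amended SAP sentence, with the matching limit on the one before it, and a changed cut-off date in programming for the affected patients. It needs no new data or visits and changes no efficacy analysis.

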6.5 SAFETY ANALYSES

The safety analyses will include all patients who received at least one dose of study drug in the Induction Phase. Separate summaries of adverse events will be provided for the open-label Induction Phase and the Maintenance Phase.

Safety will be assessed through descriptive summaries of adverse events, laboratory test results (serum chemistry, hematology including complete blood count with differential and platelet counts, and urinalysis), and the incidence of antibodies to etrolizumab.

Additional details will be provided in the SAP.

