6.5.1 Adverse Events

Verbatim descriptions of treatment-emergent adverse events will be coded and their incidence will be summarized by treatment arm, as appropriate. A treatment-emergent adverse event is defined as any new adverse event reported or any worsening of an existing condition on or after the first dose of study drug. In addition, separate summaries will be generated for serious adverse events, deaths, and adverse events leading to discontinuation of study drug. Adverse events will be summarized by mapped term, appropriate thesaurus level, and toxicity grade.

Analyses will be performed for:

- Systemic hypersensitivity events
 - Specific analyses will be performed for anaphylactic reactions using the anaphylactic reaction Sampson's criteria (see [Appendix 8](#)).
- Serious infections
 - The frequency of serious infections, in particular GI infections, will be summarized for each treatment arm.
- Opportunistic infections
 - The occurrence of opportunistic infections will be summarized for each treatment arm.
- Malignancies
 - Events that occur in the Neoplasms, Benign, Malignant, and Unspecified (Including Cysts and Polyps) System Organ Class will also be summarized for each treatment arm.
- Injection-site reactions
 - The frequency of injection-site reactions will be summarized for each treatment arm.

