**Table 1 Study Descriptions**

Study	Study Description
GA28948 (Hibiscus I) and GA28949 (Hibiscus II)	Two identical placebo-controlled induction studies assessing the efficacy and safety of etrolizumab compared to adalimumab and placebo in patients with moderate to severe active ulcerative colitis who are naive to TNF inhibitors
GA29102 (Laurel)	Placebo-controlled, maintenance study assessing the efficacy and safety of etrolizumab in patients with moderate to severe active ulcerative colitis who are naive to TNF inhibitors
GA29103 (Gardenia)	Head To Head study to evaluate the efficacy and safety of etrolizumab compared with Infliximab in patients with moderate to severe active ulcerative colitis who are naive to TNF inhibitors
GA28950 (Hickory)	Placebo-controlled, induction and maintenance study assessing the efficacy and safety of etrolizumab in patients with moderate to severe active ulcerative colitis who have been previously exposed to TNF inhibitors

TNF=tumor necrosis factor.

Studies GA28950 and GA29102 are made up of two phases: Induction Phase and Maintenance Phase. For the purpose of statistical analyses, the Induction and Maintenance Phases of Studies GA28950 and GA29102 will be treated as two independent studies and analyzed separately. Studies GA28948 and GA28949 are induction studies. Study GA29103 is a treat-through study design with no re-randomization into the Maintenance Phase; therefore, the Induction and Maintenance Phases will be analyzed as one study.

The analysis of data will be performed once all the data have been collected in the database for the primary analysis as described in the study SAPs.

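### The SAP gives maintenance adverse events and patient-years no start date except 'from baseline', which read literally puts open-label etrolizumab events in the placebo column

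*SAP*

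**What the plan says.** Study SAP Section 4.6 describes two sets of safety data. The induction set "will include data for all patients enrolled into the Induction Phase, up until they are randomized into the Maintenance Phase". The maintenance set runs until the patient completes or withdraws. No start is stated for it except the sentence "All safety analyses using the maintenance safety population data will be reported from baseline", followed by "Baseline is defined as the last available assessment prior to first receipt of study drug at the beginning of the Induction Phase".

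Three other rules bear on what the tables would contain:

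- **Columns.** Study SAP Section 4.1.2.4: "Patients will be included in the treatment arm for the treatment most frequently received during the Maintenance Phase". Induction treatment plays no part.
- **Treatment-emergent events.** Project SAP Section 4.7.1: "Treatment-emergent events are defined as any new AE reported or any worsening of an existing condition on or after the first dose of study drug". Protocol Section 6.5.1 uses the same anchor. Neither refers to the first maintenance dose.
- **Rates.** Project SAP Section 4.7.1 divides total events by total patient-years at risk and does not say when risk time begins.

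Two statements point the other way. Protocol Section 6.5 says "Separate summaries of adverse events will be provided for the open-label Induction Phase and the Maintenance Phase". Project SAP Section 1 says that the two phases of this study "will be treated as two independent studies and analyzed separately".

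**The concern.** Every patient in the maintenance safety population has already had open-label etrolizumab. If their events are counted from the pre-induction baseline and tabulated by maintenance arm, the placebo column contains events that arose on etrolizumab. The same events appear again in the induction table, which runs to randomization. The wording also reaches the dose count (study SAP 4.6.1) and the worst laboratory grade during the study (project SAP 4.7.2).

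The maintenance comparison is the only placebo-controlled safety evidence in this trial. Adding a shared etrolizumab-exposed period to both arms pulls incidence ratios and rate ratios toward 1, and shrinks the difference in the proportion of patients with at least one event. Someone reading the placebo column of the summary table could not tell which events arose on active drug.

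**Working it through.** **The plan's own figures.** The documents give no adverse event rate and no patient-years total, so there is no safety figure to reproduce. The arm size does reproduce: 350 × 0.60 / 2 = 105 per arm.

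**Doses (Schedule of Assessments, Protocol Appendix 1).** Open-label etrolizumab is given at Weeks 0, 4 and 8, which is 3 doses. Maintenance doses run every 4 weeks from Week 12 to Week 60, which is 13 doses. For a placebo-arm completer counted from baseline, 3 / 16 = 18.75% of injections in the placebo column would be etrolizumab.

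**Time.** Take 105 completers followed to Week 62. Patient-years from baseline are 105 × 62 × 7 / 365.25 = 124.8. The first 10 weeks contribute 20.1 (16.1%) and the first 12 weeks 24.1 (19.4%).

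**Rate ratio (illustrative).** Assume constant event rates, no carry-over, and the same etrolizumab rate in both phases. With *w* open-label weeks, *m* later weeks and true ratio RR, the from-baseline ratio is RR(*w* + *m*) / (*w*·RR + *m*). Follow-up ends at Week 62 for completers who enter the open-label extension. It ends at Week 60 + 12 = Week 72 for those in safety follow-up, because Protocol Section 4.5.2.4 times those visits from the last dose.

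| *w* + *m* (weeks) | RR = 2.0 appears as | RR = 3.0 appears as |
|---|---|---|
| 12 + 50 | 124/74 = 1.68 | 186/86 = 2.16 |
| 10 + 52 | 124/72 = 1.72 | 186/82 = 2.27 |
| 12 + 60 | 144/84 = 1.71 | 216/96 = 2.25 |
| 10 + 62 | 144/82 = 1.76 | 216/92 = 2.35 |

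At RR = 2.0, the share of expected placebo-column events that arose on open-label etrolizumab is 24/74 = 32%, 20/72 = 28%, 24/84 = 29% and 20/82 = 24%, in the same order.

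**A different induction rate.** Assume rates per 100 patient-years of 100 on placebo and 150 on etrolizumab in maintenance (true ratio 1.50), followed to Week 62. Each column's rate is (*w*/62) × induction rate + (1 − *w*/62) × maintenance rate. The ratio appears as 1.37 to 1.39 if the induction rate is 150, 1.29 to 1.32 if it is 300, and 1.40 to 1.42 if it is 100. The rate difference falls from 50 to between 40.3 and 41.9 in each case.

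**Patients with at least one event (illustrative).** Incidence is 1 − exp(−cumulative rate), over 12 + 50 weeks with 52 weeks to the year.

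| Events per year, etrolizumab vs placebo | Maintenance only | From baseline |
|---|---|---|
| 0.10 vs 0.05 | 9.17% vs 4.69%: 4.5 points, ratio 1.95 | 11.24% vs 6.87%: 4.4 points, ratio 1.64 |
| 0.50 vs 0.25 | 38.17% vs 21.37%: 16.8 points, ratio 1.79 | 44.91% vs 29.94%: 15.0 points, ratio 1.50 |
| 3.0 vs 1.5 | 94.41% vs 76.36%: 18.0 points, ratio 1.24 | 97.20% vs 88.17%: 9.0 points, ratio 1.10 |

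**Event counts.** At 0.50 vs 0.25 per year with 105 per arm, expected counts are 50.5 vs 25.2 in maintenance only and 62.6 vs 37.4 from baseline. The difference is 25.2 either way.

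**The case against.** The strongest reply is that the sentence was never meant as a counting rule. Baseline is defined as an assessment, and an adverse event is not reported from an assessment, whereas a laboratory change is. Study SAP Section 4.4 ties the same definition to comparisons made against baseline. On this view Section 4.6 tells programmers to use the pre-induction value as the reference, and the hand-over between phases is randomization, where the induction data stop. Protocol Section 6.5 and project SAP Section 1 support that, and the list of planned outputs, which is not among these documents, may state the window.

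That reading is plausible and may be what was intended. It does not settle the text. Section 4.6 says all safety analyses and lacks the limit used in Section 4.4. The sentence stands where the start of the data window would be expected, just after its end is given. If the benign reading is right, a start date for events and patient-years is still missing.

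Other points stand in part:

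- Project SAP Section 4.7.1 requires narratives for deaths, serious events, discontinuations due to adverse events, serious and opportunistic infections, and malignancies, so the timing of those could be recovered case by case. The summary tables would still mix the periods.
- Protocol Section 2.2 has a 62-week safety objective, so a from-baseline table has a legitimate use if labelled as such.
- The magnitudes rest on assumed rates, and the model ignores the selection of Week 10 responders into maintenance. At the lowest event rate shown, the absolute difference hardly moves.

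**Conclusion.** The concern holds. As written, the SAP assigns open-label etrolizumab events to the placebo column for placebo-randomized patients, and it conflicts with the separate summaries by phase in the protocol and the project SAP. Whether that was intended is uncertain, so confidence is moderate, but either reading leaves a gap to close.

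The 3 of 16 doses, and the 16% to 19% of a completer's time to Week 62, follow from the schedule. The diluted ratios (2.0 to between 1.68 and 1.76; 3.0 to between 2.16 and 2.35) are illustrations under constant rates without carry-over. The effect is dilution toward no difference, not reversal. The expected difference in event counts is unchanged, and type I error is not affected because safety is descriptive. It should be fixed because it touches the trial's only placebo-controlled safety comparison.

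**What to change.** In study SAP Section 4.6:

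- State that the main between-arm maintenance adverse event summary counts events with onset or worsening on or after the first maintenance dose.
- Start patient-years at risk, dose counts and worst laboratory grades on that same date.
- State that the Week 0 baseline is only the reference for change-from-baseline values.
- For patients dosed in maintenance, run the induction table to the first maintenance dose. Randomization may come up to 2 weeks earlier (Protocol Appendix 1, footnote ee), and events in that interval would otherwise fall in neither table.
- Keep a from-baseline table by arm for the 62-week objective if wanted, labelled as cumulative exposure that includes open-label etrolizumab.

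The cost is SAP wording and a stated start date in the safety programs, with no new data. The change does not create a placebo comparison for first-dose reactions, and it does not remove residual drug from the Week 8 dose.
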